6.3.1.1. Incidence of Adverse Events

All summary tables for unsolicited AEs will be provided by baseline flavivirus serostatus (flavivirus-seropositive, flavivirus-seronegative, and/or overall).

An overall summary of unsolicited TEAEs including the number and percentage of subjects who experience the following will be presented:

- Any unsolicited TEAEs
- Any serious TEAEs
- Any fatal TEAEs
- Any unsolicited medically-attended TEAEs
- Any unsolicited TEAEs leading to discontinuation from study vaccine
- Any unsolicited TEAEs leading to discontinuation from participation in the study
- Any unsolicited severe TEAEs
- Any AESI

The table will also include number and percentage of subjects with unsolicited TEAEs that are treatment-related in each of the above categories.

In addition, separate listings containing individual subject adverse event data for all unsolicited TEAEs, unsolicited TEAEs leading to discontinuation from study vaccine, unsolicited TEAEs leading to discontinuation from participation in the study, serious TEAEs, and unsolicited medically-attended TEAEs will be provided separately.

6.3.1.2. TEAEs by System Organ Class and Preferred Term

The following summary tables of TEAEs will be provided by MedDRA SOC and PT using frequency counts and percentages (i.e., number and percentage of subjects with an event):

- All unsolicited TEAEs
- All unsolicited TEAEs that are treatment-related
- All serious TEAEs
- All serious TEAEs that are treatment-related
- All unsolicited TEAEs leading to discontinuation from study vaccine
- All unsolicited TEAEs leading to discontinuation from participation in the study
- All unsolicited severe TEAEs
- All unsolicited severe TEAEs that are treatment-related
- All unsolicited medically-attended TEAEs
- All unsolicited medically-attended TEAEs that are treatment-related
- Any AESI

6.3.1.3.TEAEs by Preferred Term

The following summary tables of TEAEs will be provided by PT using frequency counts and percentages. PTs will be sorted in a descending order according to the frequency in mRNA-1893 Total group.

- All unsolicited TEAEs..
- All unsolicited TEAEs that belongs to selected SMQs (e.g. anaphylaxis, hypersensitivity, cardiomyopathy, cardiac arrhythmia, embolic and thrombotic events, cardiac failure, ischemic heart disease, autoimmune disorder, angioedema, central nervous system haemorrhages and cerebrovascular conditions). SMQs will be analyzed based on narrow and/or broad search, and details will be provided in the TLF shells.

6.3.1.4.TEAEs by System Organ Class, Preferred Term and Severity

The following summary tables of TEAEs will be provided by SOC, PT, and maximum severity (mild < moderate < severe) using frequency counts and percentages:

- All unsolicited TEAEs
- All unsolicited TEAEs that are treatment-related

6.3.1.5. Solicited Adverse Reactions

All summary tables for solicited ARs will be provided by baseline flavivirus serostatus (flavivirus-seropositive, flavivirus-seronegative, and/or overall).

An AR is any AE for which there is a reasonable possibility that the test product caused the AE. The term "Solicited Adverse Reactions" refers to selected signs and symptoms occurring after injection administration during a specified post-injection follow-up period (day of injection and 6 subsequent days). The solicited ARs are recorded by the subject in eDiary. The occurrence and intensity of selected signs and symptoms is actively solicited from the participant during a specified post-injection follow-up period (day of injection and 6 subsequent days), using a pre-defined checklist in the eDiary (i.e., solicited ARs).

The following local ARs will be solicited: pain at injection site, erythema (redness) at injection site, swelling (hardness) at injection site.

The following systemic ARs will be solicited: headache, fatigue, myalgia (muscle aches all over the body), arthralgia (aching in several joints), nausea/vomiting, fever, and chills.

The solicited ARs will be graded based on the grading scales presented in Table 13 in the protocol, modified from the Toxicity Grading Scale for Healthy Adult and Adolescent Volunteers Enrolled in Preventative Vaccine Clinical Trials (DHHS 2007). Investigator will assess Grade 4 events (with exception of fever).

If a solicited local or systemic AR continues beyond 7 days post injection, the participant will be prompted to capture solicited local or systemic AR in the eDiary until resolution.

All solicited ARs (local and systemic) will be considered causally related to vaccination.

All solicited ARs analyses will be based on Solicited Safety Set. All solicited ARs analyses will be provided by flavivirus serostatus and vaccination group as defined in Section 6.1 for each vaccination (first, second), unless otherwise specified.

The number and percentage of subjects who reported any solicited AR, any solicited local AR, and any systemic solicited AR during the 7-day follow-up period after each vaccination will be tabulated by flavivirus serostatus, vaccination group, and vaccination,

with a two-sided 95% exact CI using the Clopper-Pearson method. The same analysis will be conducted for subgroups defined by region (United States and Puerto Rico).

The number and percentage of subjects who reported each individual solicited local AR (has a severity grade of Grade 1 or greater) and solicited systemic AR (has a severity grade of Grade 1 or greater) during the 7-day follow-up period after each vaccination will be tabulated by flavivirus serostatus, vaccination group, severity grade and vaccination. The same analysis will be conducted for subgroups defined by region (United States and Puerto Rico).

The number and percentage of subjects who reported each individual solicited AR will also be summarized by flavivirus serostatus, vaccination group, severity grade, day of reporting and vaccination. The number and percentage of subjects experiencing fever (a temperature greater than or equal to $38.0^{\circ}\text{C}/100.4^{\circ}\text{F}$ by the oral, axillary, or tympanic route) by severity grade and the number and percentage of subjects experiencing a fever of Grade 3 or higher temperature (a temperature greater than or equal to $39.0^{\circ}\text{C}/102.1^{\circ}\text{F}$ by the oral, axillary, or tympanic route) in cumulative half-degree (°F) increments will be provided.

The onset of individual solicited AR is defined as the time point after each vaccination at which the respective solicited AR first occurred. The number and percentage of subjects with onset of individual solicited AR will be summarized by baseline flavivirus serostatus, vaccination group, study day relative to corresponding vaccination (Day 1 through Day 7) and vaccination.

The duration (days) of each solicited AR will be summarized by baseline flavivirus serostatus, vaccination group and vaccination number (e.g. Dose 1 and Dose 2 and 'any'). Duration will be calculated as the days of the solicited AR which is reported within the 7 days of vaccination including the day of vaccination, no matter it is intermittent or continued. The duration is calculated as end date – start date +1. If the solicited AR continues beyond 7 days, the consecutive days a solicited AR is reported after 7 days will be included (eg, an event that lasted 5 days in the first 7 days post vaccination and 3 consecutive days beyond 7 days post vaccination, the duration will be reported as 8 (5+3) days.).

All solicited ARs that continue beyond 7 days post vaccination will be presented in separate data listings.

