- Solicited local and systemic ARs (Section 11.2.3; Appendix 2) that occur on the day of each dose and during the 7 days after injection (ie, the day of injection and 6 subsequent days). Any solicited AR that is ongoing beyond Day 7 will be recorded until it is no longer reported, not to exceed 28 days after each injection. Solicited ARs recorded in eDiaries beyond Day 7 should be reviewed by study site staff either during the next scheduled telephone call or at the next study site visit (Table 1 and Table 2).
- Daily oral body temperature measurement should be performed at approximately the same time each day using the thermometer provided by the study site. If body temperature is taken more than once in a given day, only the highest temperature reading should be recorded.
- Measurements, as applicable, for solicited local ARs (injection site erythema and swelling/induration); the size measurements will be performed using the ruler provided by the study site.
- All medications taken on the day of each dose and during the 28 days after injection (ie, the day of injection and 27 subsequent days). Participants will be queried by the eDiary whether any medications were taken to treat or prevent pain or fever on a day of injection or for the 6 subsequent days.

The eDiaries will be the main source documents allowed for solicited local or systemic ARs (including body temperature measurements). Participants will be instructed to complete eDiary entries daily. If assessments are not recorded for a given day, the participant will have a limited time window on the following day to complete qualitative assessments for the previous day, excluding measurements of body temperature and of any injection site erythema or swelling/induration. Any new safety information reported during safety telephone calls or at site visits (including a solicited AR) not already captured in the eDiary will be described in the source documents as a verbally reported event. Any solicited AR reported in this manner must be entered on the Reactogenicity page of the eCRF.

Procedures for transferring eDiary data to the eCRF are presented in the Study mRNA-1893-P201 Study Manual. Study site staff will review eDiary data with participants at the Day 8 and Day 36 Visits.

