5.2. Solicited Safety Set

The Solicited Safety Set consists of all participants who are randomly assigned and received any IP and contribute any solicited AR data. The Solicited Safety Set will be used for the analyses of solicited ARs and participants will be included in the treatment arm corresponding to the IP they actually received.

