6.1. General Considerations

The Schedule of Assessments is provided in Appendix E for the vaccination period and the follow-up period, and Appendix F for the extension period.

Continuous variables will be summarized using the following descriptive summary statistics: the number of subjects (n), mean, standard deviation (SD), median, minimum (min), and maximum (max).

Categorical variables will be summarized using counts and percentages.

Baseline value, unless specified otherwise, is defined as the most recent non-missing measurement (scheduled or unscheduled) collected before the first dose of IP. For immunogenicity tests, the baseline is defined as the most recent non-missing measurement (scheduled or unscheduled) collected before or on the date of first dose of IP.

For the summary statistics of all numerical variables unless otherwise specified, the display precision will follow programming standards. Please see Appendix A for variable display standards.

When count data are presented, the percentage will be suppressed when the count is zero in order to draw attention to the non-zero counts. A row denoted "Missing" will be included in count tabulations where specified on the shells to account for dropouts and missing values. The denominator for all percentages will be the number of subjects in that vaccination group within the analysis set of interest, unless otherwise specified.

Study day relative to the first injection will be calculated as below:

a) study day prior to the first injection will be calculated as: date of assessment/event
 date of the first injection;

b) study day on or after the date of the first injection will be calculated as: date of assessment/event – date of the first injection + 1;

Study day relative to the most recent injection will be calculated as below:

- a) study day prior to the first injection will be calculated as: date of assessment/event
 date of the first injection;
- b) study day on or after the date of the first injection but before the second injection (if applicable) will be calculated as: date of assessment/event date of the first injection + 1;
- c) study day on or after the date of the second injection will be calculated as: date of assessment/event – date of the second injection + 1; if study day is on the same day as the second injection, date and time will be compared with the second injection date and time.

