For calculation regarding antibody titers/antibody concentrations, antibody values reported as below LLOQ will be replaced by 0.5 × LLOQ. Values that are greater than the upper limit of quantification (ULOQ) will be converted to the ULOQ. Missing results will not be imputed.

The following stages for safety analyses will be used in this study:

- Up to 28 days after any vaccination: this stage starts at the day of each vaccination
 and continue through the earliest date of (the day of each vaccination and 27
 subsequent days, next vaccination [if applicable]). This analysis period will be used
 as the primary analysis period for safety analyses including unsolicited AE, except
 for solicited AR, unless specified otherwise.
- Up to 28 days after the first vaccination.
- Up to 28 days after the second vaccination.
- Overall stage: this analysis period starts at the first injection on Day 1 and continues through the earliest date of (study completion, discontinuation from the study, or death).

Unscheduled visits: Unscheduled visit measurements will be included in analysis as follows:

- In scheduled visit windows per specified visit windowing rules.
- In the derivation of baseline/last on-treatment measurements.
- In the derivation of maximum/minimum on-treatment values and maximum/minimum change from baseline values for safety analyses.
- In individual subject data listings as appropriate.

Visit windowing rules: The analysis visit windows for protocol-defined visits are provided in Appendix B.

Incomplete/missing data:

- Imputation rules for missing prior/concomitant medications, non-study vaccinations and procedures are provided in Appendix C.
- Imputation rules for missing AE dates are provided in Appendix D.
- For laboratory assessments, if majority of results are indefinite, imputation of these values will be considered. If the laboratory results are reported as below the LLOQ (e.g., <0.1), the numeric values will be imputed by 0.5 × LLOQ in the summary. If the laboratory results are reported as greater than the ULOQ (e.g., >3000), the numeric values will be imputed by ULOQ in the summary.
- Other incomplete/missing data will not be imputed, unless specified otherwise.

Treatment groups:

The following vaccination groups will be used for summary purposes:

- mRNA-1893 vaccine: μg (2-dose)
- mRNA-1893 vaccine: CCI μg (2-dose)
- mRNA-1893 vaccine: μg (single-dose)
- mRNA-1893 vaccine: Total
- Placebo

Summary by flavivirus serostatus:

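### By-day solicited reaction percentages are divided by the whole Solicited Safety Set, so missing diary entries pull them down

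*SAP*

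**What the plan says.** SAP 6.1 sets a general rule: "The denominator for all percentages will be the number of subjects in that vaccination group within the analysis set of interest, unless otherwise specified". SAP 6.3.1.5 names the set for this family of tables: "All solicited ARs analyses will be based on Solicited Safety Set". SAP 5.2 admits to that set any randomized participant who "received any IP and contribute any solicited AR data", so membership is not specific to an injection, a day or a symptom.

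SAP 6.3.1.5 then plans percentages for each symptom over the 7-day period by severity grade, and states that each individual reaction "will also be summarized by flavivirus serostatus, vaccination group, severity grade, day of reporting and vaccination". It gives no other denominator for these tables. Elsewhere the SAP does override its default: in 6.2.1, completion of the extension period is a percentage of those who consented to enter it.

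On missing data, SAP 6.1 has no diary-specific rule; the general one is "Other incomplete/missing data will not be imputed, unless specified otherwise". Protocol 8.5.1 allows a missed diary day to be completed on the following day for qualitative items, "excluding measurements of body temperature and of any injection site erythema or swelling/induration". The same section requires a solicited reaction that is reported verbally and is absent from the diary to be entered on the Reactogenicity page of the eCRF.

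**The concern.** A percentage for one symptom on one day should be taken over the people whose status on that day is known. Here it is taken over everyone who ever contributed solicited data. Protocol 8.5.1 has the first entry after each injection made under site supervision, so almost every injected participant will qualify for the set. Later entries are made at home. A participant who stops recording after the clinic entry remains in the denominator for the rest of the week.

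Solicited reactions are a primary safety endpoint, and the trial is meant to select the Phase 3 dose level (protocol 4.2). Protocol 2.3.2 reports fever after the second injection in 29.2% at one of the two dose levels carried forward (7 cases, 2 of them Grade 3), and a trend to more erythema and swelling at higher dose levels. Those measured reactions are the ones that the diary cannot back-fill.

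**Working it through.** The plan states no figure that depends on this denominator, so there is nothing to reproduce. The check has three steps.

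**Inputs**
- Denominator and set: SAP 6.1, 5.2 and 6.3.1.5.
- Arm size: 200 planned (SAP 4.1).
- Phase 1 fever after injection 2: 29.2% (7/24 = 29.2%), protocol 2.3.2. This is a rate per injection, not per day, so it is used only in step 3.
- q, the share of the set with no entry for a given symptom and day: not in the documents. Assumed 0.05, 0.10 and 0.20, unrelated to symptoms and with no verbal recovery.

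**Step 1: by-day table**

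Reported rate = true rate × (1 − q), so the ratio of reported to true is 0.95, 0.90 and 0.80. The relative understatement equals q.

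In counts, take 200 participants, q = 0.10 and, for illustration only, 52 with the reaction that day:
- Whole-set denominator: 52/200 = 26.0% (Clopper-Pearson 95% CI 20.1 to 32.7).
- Participants with an entry: 200 × 0.90 = 180, and 52/180 = 28.9% (22.4 to 36.1).

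**Step 2: measured against qualitative items**

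Next-day completion can lower q for qualitative items but not for temperature, erythema or swelling. If it took q from 0.10 to 0.05 for the former (assumed), the ratios would be 0.95 for qualitative and 0.90 for measured items in the same table.

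**Step 3: 7-day table**

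Two mechanisms need separating.

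(a) Let z be the share of the set with no data for that symptom after that injection, including anyone who did not receive injection 2. Reported rate = true rate × (1 − z). At an assumed z = 0.05, 29.2% × 0.95 = 27.7%. A denominator change corrects this.

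(b) Isolated missed days affect the any-occurrence rate only if every day of the reaction was missed (a severity table can also lose the worst grade). With days missing independently:

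| Fever lasts | q = 0.10 | q = 0.20 |
|---|---|---|
| 1 day: 29.2% × (1 − q) | 26.3% | 23.4% |
| 2 days: 29.2% × (1 − q²) | 28.9% | 28.0% |

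A denominator of participants with at least one entry hardly moves these figures. The chance of no entry on all seven days is q⁷: 0.0000001 at q = 0.10 and 0.0000128 at q = 0.20. The one-day-fever rates would still read 26.3% and 23.4%.

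**The case against.** The strongest reply has four parts.

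**Verbal reports.** A missing diary day is not necessarily lost. Staff review the diary with participants at Days 8 and 36, just after each 7-day window, and a reaction reported then goes on the eCRF. This stands, and it is why the understatement is up to q and not exactly q. Recovery is partial, because a temperature or diameter that was not taken cannot be measured later.

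**Unseen shells.** SAP 6.1 lets the default be overridden and allows a Missing row where the shells call for one. The shells are not among the documents and may do either. But the SAP text contains no override for these tables, and a Missing row would show the gap without changing the percentage.

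**By-day tables are secondary.** The primary endpoint covers the 7-day period, and the study tests no hypothesis. This stands and limits the weight of the point. A reader might infer from the arithmetic that the 7-day fever rate would fall from 29.2% to 26.3% and that a new denominator would restore it. The documents support neither. The fall requires one-day fevers on missed days that are never reported verbally, and step 3(b) shows that the new denominator leaves it in place.

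**No bias between arms is shown.** A reader might also infer a distorted dose comparison. Two arms with a true 29.2% and with 5% and 15% missing would report 27.7% and 24.8%, a false gap of 2.9 points. Nothing in the documents indicates that completion differs by arm, and a common q leaves ratios between arms unchanged.

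**Conclusion.** The point holds for the by-day tables, and for the lack of an injection-specific and symptom-specific denominator in the 7-day tables. As written, the plan understates by-day percentages by up to q in relative terms, with a larger q for the measured reactions. The direction follows from the SAP text if missing entries are unrelated to symptoms; the size cannot be known, because no completion rate is given. In the 7-day tables the correctable part equals the share with no data for that symptom after that injection, also unknown.

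It would go too far to say that a blank diary day is always counted as no reaction. That is a consequence of the arithmetic and not a written rule, and it does not apply where the event reaches the eCRF. This is a minor point that is cheap to settle.

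**What to change.** In SAP 6.3.1.5, state the denominators explicitly:
- **By-day tables:** participants with a non-missing entry, or a verbally reported event, for that symptom, day and injection.
- **7-day tables:** participants with at least one entry or reported event for that symptom after that injection.
- **All of these tables:** print n and the number missing beside each percentage.

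The text should not claim that the 7-day change recovers reactions on isolated missed days.

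The cost is SAP wording and a shell change, with no new data. Denominators will vary by symptom and day. The by-day percentage will assume that missing days resemble recorded ones; if participants who feel well skip entries, it will read high. Verbally reported events add to numerator and denominator together, which also pushes the percentage up slightly, so their number should be shown.

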6.3.2. Pregnancy Tests

A point-of-care urine pregnancy test will be performed at the Screening Visit (Day 0) and before each vaccine dose. At any time, a pregnancy test either via blood or point-of-care urine can be performed, at the discretion of the investigator. A by-subject listing will be provided for pregnancy tests.

6.3.3. Vital Sign Measurements

Vital sign measurements, including systolic and diastolic blood pressures, pulse respiratory rate, and body temperature, will be presented in a data listing. The values meeting the toxicity grading criteria will be flagged in the data listing. The abnormalities meeting the toxicity grading criteria (Grade 3 or higher) in any vital sign measurement provided by Table 14 in the protocol will be listed separately. If a subject has a vital sign result with Grade 3 or higher abnormality at any post injection visit, then all results of vital sign measurement for that subject will be presented in the listing. Note that vital signs grading are derived based on the numerical values only.

Observed values and changes from baseline for all vital sign measurements will be summarized at each scheduled visit by flavivirus serostatus and vaccination group as defined in Section 6.1. Shift from baseline in the toxicity grades will also be summarized at each scheduled visit by flavivirus serostatus and vaccination group.

